9.4.2. Details of data sources

In order to meet the study objectives, the following data sources will be considered:

France – SNDS

The French National Health Data System (SNDS) is the largest and most comprehensive healthcare dataset available in Europe with a 10-year longitudinal follow-up for more than 50 million patients. SNDS includes anonymized administrative and healthcare claims data from the French national health care insurance system databases. In particular data from SNIIRAM (Système national d'information interrégimes de l'Assurance maladie) which consist of: hospital discharge summaries (Programme de Médicalisation des Systèmes d'Information, [PMSI]), all outpatients reimbursed health expenditures (données de consommation inter-régimes, [DCIR]), and national death registry (CépiDC database on causes of death) (9). SNDS data consist of anonymized data of reimbursed claims for all patients affiliated with compulsory health insurance providers (the general scheme covers about 86% of France residents, and 14 other schemes cover the rest) and cover about 99% of French residents.

Data from DCIR and PMSI have been linked for each patient to allow for follow-up across different settings of care including outpatient practice and hospital admissions related to medicine, surgery and obstetrics. At this time, date of death from the national death registry is linked to the other data for all the periods. Causes of death are progressively integrated (only available for 2013, 2014, and 2015). Healthcare use of the patient can then be tracked since birth/first residence in France for 10 years even if a subject is not working, changes occupation or retires and irrespective of socio-economic status. There is no loss to follow-up except for emigration.

For more information see [Annex 3](#).

Denmark – National Registers

The Danish data sources for this study are owned, run and made accessible to research projects by Danish governmental and regional authorities (10). The Danish health care system is a tax-funded, one-payer system with full coverage for all residents (5.8 million) and some co-payment from the patients for prescriptions drugs and dental work.

Since introducing the Danish Civil Registration System in 1968, information on demographics (age, sex, and geographical region), migration and vital statistics data has been registered electronically on a daily basis for all Danish residents. Every individual in Denmark is provided with a unique personal identification number (PIN) at birth or upon immigration which allows for follow-up until death or emigration. The PIN forms the basis for the precise, deterministic linkage of individual-level data between all patient-level registers and databases in Denmark, allowing the creation of a study database with individual-level data for any given study. The PIN also allows for family linkage of data.

At least the following national registers are important for this study:

- Danish Register of Medicinal Products Statistics (RMPS)

- Danish Hospital Patient Medication Register (SMR)
- Danish National Patient Register (DNPR)
- Danish Register of Causes of Death

For more information see [Annex 3](#).

Sweden – National Registers

Every individual in Sweden is provided with a unique PIN at birth or upon immigration which allows for follow-up until death or emigration. The PIN is used for many administrative purposes, such as an identifier in population and health care registers.

The patient-level data can be linked across registers using the PIN assigned to each citizen or permanent resident of Sweden. The PIN is a ten-digit number used as a unique identifier for a multitude of purposes, such as communication with government agencies, maintaining personal information in population-based registers and to keep track of patients and their medical records. The PIN has three parts: date of birth, a three-digit sex-specific birth number and a control digit. Using the control digit, errors to the date of birth or birth number can be detected. Once assigned, a person (usually) retains the same PIN throughout their lifetime. Thus, the registers are a mirror of clinical practice in Sweden. Furthermore, the data sources are also used extensively for epidemiological research.

At least the following national registers are important for this study:

- Swedish Prescribed Drug Register
- Swedish National Patient Register (NPR)
- Swedish Cause of Death Register

For more information see [Annex 3](#).

Spain – SIDIAP

The SIDIAP (Sistema d'Informació per al Desenvolupament de l'Investigació en Atenció Primària) is a longitudinal patient-level Electronic Medical Records (EMR) database that contains anonymised healthcare data from the primary care setting in Catalonia. The database includes 279 of 370 primary care centres in Catalonia and represents a population of around 5.6 million people and approximately 74% of the Catalan population.

The database contains information collected by healthcare professionals during routine visits in primary care. It includes individual data on patients' demographics (age, gender) and other characteristics (e.g., smoking status); clinical measurements such as body mass index or blood pressure; diagnoses (incl. ICD-10 code, date); prescriptions (incl. ATC code, duration, daily dose); healthcare contacts (visits in primary care, referrals); diagnostic procedures and laboratory tests and sick leave. For all patients, information available in the database is linked to a unique anonymous identifier. Information on drugs prescribed by a professional of the Catalan Institute of Health and

dispensed in pharmacies is available. For studies requested by the EMA, SIDIAP data can also be linked with hospital discharge data and hospital dispensation medication capturing most of the drugs administered in hospitals.

The SIDIAP is highly representative of the population of Catalonia in terms of geographical, age, and sex distributions (11). The database has been used extensively in medical research, including DUS, since 2010 and across Europe, and has been found to be a valid source for research (12). Moreover, several recent studies have been conducted in SIDIAP on oral anticoagulant therapy (13-18).

9.5. Study size

9.5.1. Estimation of sample size

This study is descriptive in nature with no intent for hypothesis generating or testing, and thus does not require power calculation. This study will be conducted on several data sources from different countries, with different degree of coverage, and all patients fulfilling inclusion and exclusion criteria will be analysed.

The sample size estimation according to different levels of precision and proportion of interest is proposed below. The size of the sample population will determine the precision of the estimations, measured as the range of their 95% CI. The assumptions for the precision estimation are based on the results of bleeding and recurrent VTE events from the pivotal Phase III EINSTEIN Junior study (6). The incidence of CRNM bleeding among children under two years old was 5.6% with rivaroxaban and 5.9% with comparator, while the incidence of recurrent VTE among children was 1.2% and 3.0% for rivaroxaban and comparator, respectively.

Table 5 shows the required number of patients by acceptable precision (95% CI) and proportions of interest using the exact approximation formula for CI for proportions.

For example, for an outcome with an incidence of 5%, at least 94 patients are required for a precision of 5% for the 95% CI, and 29 patients are required for a precision of 10%.

Table 5: Required number of patients by acceptable precision (95% CI) and proportions of interest using the exact approximation formula for CI for proportions

Proportion of interest	Margin of error for 95% CI (absolute precision)		
	5%	7.2%	10%
0%	35	24	17
1%	43	28	19
3%	67	37	23
5%	94	50	29
8%	133	68	38
10%	157	80	43

CI = Confidence interval

Exact approximation formula according to the Clopper-Pearson method.

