9.2.2. Study time frame

9.2.2.1. Index date and follow-up

The index date will be the day of initiation of any anticoagulation therapy (rivaroxaban oral suspension or SOC). Patients will be assigned to two exposure categories, rivaroxaban or SOC, according to their actual use of the respective anticoagulation therapy. They may contribute time at risk to more than one exposure category if they switch from one to the other. More specifically, patients will be allowed to switch multiple times between SOC and rivaroxaban and contribute time accordingly to both exposure categories, as long as the same anticoagulant treatment period is continuing.

Patients will be followed from the index date to the earliest of the following censoring criteria:

- End of the anticoagulation treatment period, i.e., discontinuation of all study drugs (rivaroxaban and SOC),
- Death,
- Disenrollment/de-registering/emigration or last available data,

- End of the study period.

Moreover, patients will be followed until the first occurrence of each safety/effectiveness outcome event, with time at risk defined separately for each outcome analysis.

If patients have another initiation of anticoagulant therapy (SOC or rivaroxaban) for a VTE diagnosis before the age of two years, i.e., another qualifying anticoagulant treatment period for a recurrent VTE observed during the inclusion period for which they fulfil all inclusion and exclusion criteria (including a 6-month washout period), they will be allowed to enter the study cohort again, with a new index date.

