9.5.3. Monitoring of actual patient counts

The number of patients for the study population that accrue in the data sources will be monitored over time in order to decide when to launch the analyses.

The strategy for this monitoring will depend on the two following data source conditions:

- In data sources where patient count and/or data extraction is feasible before the study conduct itself, the actual number of children with VTE receiving rivaroxaban oral suspension will be monitored annually, per calendar year and cumulatively.
- In data sources where this is not feasible, patient counts as estimated in [Section 9.5.2](#) will be updated based on the actual sales data of rivaroxaban oral suspension.

These actual patient count estimates will be reported annually for each data source as part of progress reports.

Based on the patient count estimates (see [Section 9.5.2](#)) and the required number of patients for a precision level of 10% for the 95% CI of an outcome with a 5% incidence (see [Section 9.5.1](#)), it is anticipated that the study should last at least seven years (inclusion period from 2021 to 2026 with follow-up until end of 2027) to include at least 29 children under two years with VTE and receiving rivaroxaban oral suspension per data source. As explained above, the total of those patients in the four countries is expected to be approximately 280.

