9.7.4. Safety and effectiveness outcomes

Analyses of outcomes will be conducted according to anticoagulation therapy received: rivaroxaban and SOC (including heparins, VKAs, and other DOACs).

Time at risk will consider the exposure of interest (rivaroxaban or SOC) according to the as-treated assumption. For each outcome, the first occurrence for that outcome during time at risk will be identified.

The primary analysis of major bleeding will be based on the outcome definition considering all bleedings at critical sites (or requiring transfusion or resulting in death). A secondary analysis will be based on an analysis per bleeding site if numbers permit.

For each exposure category:

- A crude incidence rate with corresponding 95% CI will be estimated for each outcome.
- The cumulative incidence with 95% CI of each outcome will be estimated at regular time intervals (e.g., at 3, 6, 9 and 12 months).
- Event-free survival of each outcome will be presented graphically with the Kaplan-Meier method.

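### The 10% precision claimed for 29 children per data source belongs to a fully observed proportion, not to the censored, person-time bleeding estimates the protocol plans

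*Protocol*

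**What the plan says.** Protocol section 9.5.1 equates study size with precision, "measured as the range of their 95% CI", and takes its reference incidences from the pivotal paediatric trial (bleeding 5.6% and 5.9%). Table 5 gives the required numbers "using the exact approximation formula for CI for proportions" and is footnoted "Exact approximation formula according to the Clopper-Pearson method". The worked example reads "for an outcome with an incidence of 5%, at least 94 patients are required for a precision of 5% for the 95% CI", and gives 29 for a precision of 10%.

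Section 9.5.3 bases the study length of at least seven years on the patient count estimates and on the "required number of patients for a precision level of 10% for the 95% CI of an outcome with a 5% incidence", with 29 rivaroxaban children per data source as the minimum.

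The analysis is of a different kind. Section 9.7.4 plans a crude incidence rate, Kaplan-Meier curves, and this: "The cumulative incidence with 95% CI of each outcome will be estimated at regular time intervals (e.g., at 3, 6, 9 and 12 months"). Time at risk is as-treated. Section 9.2.2.1 lists as the first censoring event "End of the anticoagulation treatment period, i.e., discontinuation of all study drugs (rivaroxaban and SOC"). Under sections 9.3.1 and 9.7.6.1, a switch between rivaroxaban and standard of care moves the child's time to the other category, and 30 days of carry-over are added only where no switch occurs.

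No section gives an expected interval for a rate or for a cumulative incidence at a time point.

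**The concern.** A Clopper-Pearson interval assumes one yes/no result per child, all observed to the end. Neither planned bleeding estimate has that form. The width of a rate's interval depends on events and person-time, and a margin of 10 percentage points has no direct meaning for it. The width of a cumulative incidence interval depends on how many children are still on the drug as the time point approaches.

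Bleeding is a primary objective of a study requested to address bleeding risk in the youngest children. A reader of sections 9.5.1 and 9.5.3 will take the 10% as the precision with which rivaroxaban bleeding will be known in each source. It is not, and no applicable figure is given elsewhere, including for SNDS, the one source where the protocol expects outcome analysis to be feasible.

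**Working it through.** **1. Reproducing Table 5.** With x = np, L = Beta⁻¹(0.025; x, n−x+1) and U = Beta⁻¹(0.975; x+1, n−x), I took the smallest n with (U−L)/2 no larger than the margin. For p = 5% this gives 94, 50 and 29, as printed, and all 18 cells agree within one patient. Reading precision as the full width gives 334, 170 and 94, so the table means half-width.

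**2. Slack at 29.** x = 1.45, L = 0.3%, U = 20.1%, half-width 9.9 points. At n = 28 it is 10.1. The figure has no room for censoring.

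**3. Cumulative incidence with censoring.** The documents give no distribution of time on treatment and no timing of bleeds. Section 7.2 gives only a suggested range for idiopathic VTE, from at least 3 months to at most 6 to 12. The following are therefore my assumptions: mean treatment 3 or 6 months, exponential or gamma (shape 3), plus one month of carry-over, with constant hazard h.

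- Expected Greenwood variance: Var = S(t)² × ∫₀ᵗ h du / [n S(u) G(u)], where G is the probability of still being on treatment or in carry-over.
- Effective n = S(1−S)/Var, then the Clopper-Pearson half-width at that n.

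Worked case: n = 29, 5% by 12 months, exponential mean 6, no carry-over. h = −ln(0.95)/12 = 0.00427 per month. The integral without n is 0.1695. Var = 0.9025 × 0.1695/29 = 0.00527. Effective n = 0.0475/0.00527 = 9.0, and the half-width is 20.4 points. With carry-over, effective n is 10.6 and the half-width 18.4 points, with about 4 children at risk.

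Half-widths in points at 3/6/9/12 months, carry-over included:

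| n | Risk | Exponential, mean 6 | Gamma, mean 6 | Exponential, mean 3 | Gamma, mean 3 |
|---|---|---|---|---|---|
| 29 | 5% by 12 months | 7.8/10.7/14.1/18.4 | 7.2/9.3/13.0/19.9 | 8.7/14.8/24.6/37.5 | 7.6/15.0/39.4/not estimable |
| 219 | 5% by 12 months | 1.9/2.9/4.1/5.5 | 1.8/2.6/3.8/5.9 | 2.1/3.8/6.7/11.5 | 1.9/3.9/11.7/40.0 |
| 219 | 5% per 3 months | 3.3/5.1/7.0/9.1 | 3.2/4.6/6.5/9.8 | 3.6/6.5/11.0/17.8 | 3.3/6.6/17.7/44.3 |

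Other assumptions:

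- Without carry-over, the worst 6-month value at n = 219 is 9.6 (Weibull shape 2, mean 3, higher hazard).
- Longer treatment (exponential median 6 months, no carry-over, 5% by 12 months) gives 15.9 at 12 months for n = 29. Holding 10 points there would take about 64 children, or about 159 with a median of 3 months.
- If all bleeds fall within the first 3 months, n = 29 gives 10.2 to 12.4 at every time point, and n = 219 gives 3.2 to 3.8.
- As a check by another measure, 1.96 × SD of a simulated Kaplan-Meier estimate (5.6% by 12 months, n = 29, no carry-over) was 16 to 24 points at 12 months.

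**4. Rate.** Table 6 expects 12 rivaroxaban bleeds in SNDS (219 × 5.6% = 12.3), with a range of 5 to 20. Exact Poisson limits are χ²(0.025; 2d)/2 and χ²(0.975; 2d+2)/2. For d = 12 they are 6.2 and 21.0, or 0.52 to 1.75 times the estimate. For d = 5 the factors are 0.32 to 2.33, and for d = 20 they are 0.61 to 1.54.

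**The case against.** The study is descriptive, has no power calculation and analyses every eligible child, so Table 5 does not limit inclusion. Sections 9.5.2 and 9.7.8 expect bleeding analyses to be feasible only in SNDS, where numbers are far above 29. The time points are given as examples, and detailed analysis is deferred to the SAP. All of this stands. It limits the consequence but not the mismatch, because the precision claim and its use to justify duration are in protocol text.

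A reader might go further in three ways that the documents do not support:

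- **That 10% fails at most planned time points.** This depends on durations and hazards that the protocol does not give, and it is not universal even at 29: the 3-month value is within 10 points in all four carry-over scenarios with 5% risk by 12 months. At 219 it is wrong for 3 and 6 months under everything tried. A hazard of 5% per 3 months also raises the 12-month risk to 18.5%, so part of the widening comes from a larger proportion and not from censoring.
- **That the protocol expects about 3 months of treatment.** Section 9.7.3 only sets reporting categories at 3 months.
- **That late risks resting on a handful of children will be published.** Section 9.7.8 requires small counts to be suppressed, and Table 4 marks bleeding as below threshold outside SNDS.

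The choice of headline time point or a minimum number at risk is mostly a matter for the SAP.

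**Conclusion.** The concern holds in limited form. Table 5 is arithmetically sound for a fully observed proportion, but the 10% attached to 29 children is not the precision of either planned bleeding estimate. That mismatch needs no assumption.

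Its size does. At 29 children and 5% risk by 12 months, the 12-month half-width is roughly 18 points or more if mean treatment is 3 to 6 months, and somewhat less if treatment is longer. At 219 children in SNDS, 10 points is met at 3 and 6 months throughout, and may be missed at 9 and/or 12 months if treatment is short or the hazard is high. The planned analyses themselves are not invalidated. What needs correcting is the stated precision and its role in section 9.5.3.

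**What to change.** In sections 9.5.1 and 9.5.3, state that Table 5 applies only to a simple proportion with complete follow-up, and withdraw the 10% claim for the bleeding estimates. In its place give, at the expected SNDS size (219, range 81 to 356):

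- the exact Poisson interval for the rate (12 expected events: 0.52 to 1.75 times the estimate), with the expected person-time;
- the expected interval for cumulative incidence at each time point, under a stated treatment-duration assumption that includes the 30-day carry-over.

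Show later time points with numbers at risk, subject to the suppression rules.

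The cost is protocol wording and a short calculation, with no extra patients. The downside is that the stated precision becomes less favourable and late time points may prove uninterpretable.

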9.5.2. Estimation of patient counts

It is assumed that four countries will be targeted to collect the data from the respective country's data source. The actual study size will depend on the number of final selected data sources, product uptake over time and study duration. All paediatric patients from the target population present in the selected data sources will be analysed. An estimation of patient counts is provided in [Table 6](#). The method to estimate the patient count comprised two steps:

- First step consisted in estimating the cumulative number of children under two years with VTE in each data source over an inclusion period of 2021-2026. This estimation was based on the following parameters: i) the incidence rate of VTE in the general paediatric population, ranging from 0.14 to 0.49 per 10,000 patients (2); ii) the percentage of patients under two years among children with VTE, ranging from 20% to 25% (19); iii) the population size of children in each country; and iv) the data source coverage in each country. The cumulative number of children under two years with VTE were provided for each data source with three estimates: the lowest estimate was based on incidence rate of VTE of 0.14/10,000 and 20% of children under two years among children with VTE; the highest estimate was based on incidence rate of VTE of 0.49/10,000 and 25% of children under two years among children with VTE; finally, an average estimate was reported as the mean of the lowest and the highest estimates. For instance, the average estimate of the cumulative number of children under two years with VTE included over 2021-2026 ranges from 45 children in SIDIAP in Spain to 650 children in SNDS in France.
- Second step consisted in estimating the number of those paediatric patients exposed to rivaroxaban oral suspension. This estimation was based on assumptions of market share of the product over the period of 2021-2026: 10% in 2021, 32% in 2022, 38% in 2023, 42% in 2024, 50% in 2025 and 30% in 2026. Similarly, to the first step, a lowest, a highest and an average estimate were provided for each data source. As a result, the average estimate of the cumulative number of children under two years with VTE and exposed to rivaroxaban oral suspension ranges from 15 patients in SIDIAP in Spain to 219 patients in SNDS in France.

Then, for each data source and population (i.e., overall study population and subgroup of patients with rivaroxaban oral suspension), the lowest, highest, and average number of expected outcomes were estimated by using the incidence rates of the pivotal Phase III EINSTEIN Junior study as reference for the CRNM bleeding (5.6% with rivaroxaban, 5.9% with comparator) and the VTE events (1.2% with rivaroxaban, 3.0% with comparator).

Over 2021-2026, an average of 650 children under two years with VTE would be identified in the SNDS (range from 242 to 1058), with an average of 219 of them (range 81-356) using rivaroxaban oral suspension, and an average of 12 of them (range 5-20) having a bleeding with hospitalization. In the Swedish national registers, this would lead to an average total of 98 children under two years with VTE (range 37-160), with 33 of them receiving rivaroxaban oral suspension (range 12-54), and 2 of them with a bleeding with hospitalization (range 1-3). In the Danish national registers, an average total of 52 children under two years with VTE (range 19-85) is expected, with 18 of them receiving rivaroxaban oral suspension (range 7-29), and 1 of them with a bleeding with hospitalization (range 0-2). In SIDIAP, we could expect an average total of 45 children under two

years with VTE (range 17-73), with 15 of them receiving rivaroxaban oral suspension (range 6-25), and 1 of them with a bleeding with hospitalization (range 0-1).

Based on these patient count estimations, the expected total study size in the four target countries (Denmark, France, Spain, and Sweden) is about 850 children under two years with VTE, with approximately 280 of them using rivaroxaban oral suspension.

Of note, small cell counts must be suppressed in results from all data sources to mitigate the risk of re-identification. Due to the small sample size and low frequency of the outcomes, it is expected that the outcomes analysis with respect to bleedings and recurrent VTE should only be feasible in the SNDS (as shown in [Table 6](#)).

Table 6: Estimation of patient counts

Country - Data source(s)	Denmark national registers	France SNDS	Spain SIDIAP	Sweden national registers	Overall
Children <2y with VTE^a					
Annual number					
Lowest estimate	3	40	3	6	52
Highest estimate	14	176	12	27	229
Average estimate	9	108	7	16	141
Cumulative number of patients over 2021-2026					
Lowest estimate	19	242	17	37	315
Highest estimate	85	1058	73	160	1376
Average estimate	52	650	45	98	846
Cumulative number of outcomes over 2021-2026^b					
Bleeding with hosp. - Lowest estimate	1	14	1	2	18
Bleeding with hosp. - Highest estimate	5	61	4	9	79
Bleeding with hosp. - Average estimate	3	37	3	6	49
Recurrent VTE - Lowest estimate	0	5	0	1	7
Recurrent VTE - Highest estimate	2	22	2	3	29
Recurrent VTE - Average estimate	1	14	1	2	18
Children <2y with VTE and receiving rivaroxaban granules for oral suspension^c					
Cumulative number of patients over 2021-2026					
Lowest estimate	7	81	6	12	106
Highest estimate	29	356	25	54	463
Average estimate	18	219	15	33	285
Cumulative number of outcomes over 2021-2026^b					
Bleeding with hosp. - Lowest estimate	0	5	0	1	6
Bleeding with hosp. - Highest estimate	2	20	1	3	26
Bleeding with hosp. - Average estimate	1	12	1	2	16
Recurrent VTE - Lowest estimate	0	1	0	0	1
Recurrent VTE - Highest estimate	0	4	0	1	6
Recurrent VTE - Average estimate	0	3	0	0	3

CRNM = Clinically relevant non-major; SIDIAP = Sistema d'Informació per al Desenvolupament de l'Investigació en Atenció Primària; SNDS = Système National Des Données De Santé; VTE = Venous thromboembolism

Counts in red are below disclosure threshold.

^a Lowest estimate based on incidence rate of VTE of 0.14/10,000 and 20% of children under two years among children with VTE. Highest estimate based on incidence rate of VTE of 0.49/10,000 and 25% of children under two years among children with VTE. Average estimate is the mean of lowest and highest estimates.

^b Based on respective estimate of patients' number and outcome incidence from EINSTEIN JR: 5.6% (rivaroxaban) and 5.9% (comparator) for bleeding with hospitalization (major + CRNM bleedings); 1.2% (rivaroxaban) and 3.0% (comparator) for recurrent VTE.

^c Based on market share scenario for rivaroxaban oral suspension: 10% in 2021, 32% in 2022, 38% in 2023, 42% in 2024, 50% in 2025 and 30% in 2026.

